3.3.2.3 Rationale for Preferential Venetoclax Dose Modifications in the Setting of Overlapping Toxicities

Dose delays and dose modifications as a result of adverse events should proceed on the basis of the principle of maintaining the dose intensity of atezolizumab, carboplatin, and etoposide. The determination of dose modifications will be made on the basis of the investigator's assessment of ongoing clinical benefit with continuing study treatment in consultation with and with the approval of the Medical Monitor.

In the event of high-grade hematologic toxicities such as neutropenia, febrile neutropenia, thrombocytopenia (overlapping toxicities for venetoclax and carboplatin etoposide), and high-grade gastrointestinal toxicities such as diarrhea (overlapping toxicity for venetoclax, atezolizumab, carboplatin, and etoposide), the dose of venetoclax should be reduced as per Table 6. The dose of carboplatin and etoposide should be reduced per standard guidance provided in Table 7. No dose reduction of atezolizumab is permitted in the study.

In each specific portion of study treatment (induction vs. maintenance), no re-escalation of venetoclax dose is allowed after dose reduction. The dose level of venetoclax in the maintenance portion (RP2D-M) identified in Arm A will not be affected by venetoclax dose reductions during the induction phase. The dose of carboplatin and etoposide can be re-escalated (even to full dose) with the approval of the Medical Monitor. For more details, see Sections 5.1.5 and 5.1.6.

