Dose interruptions for reason(s) other than adverse events, such as surgical procedures, may be allowed with Medical Monitor approval. The acceptable length of interruption will depend on agreement between the investigator and the Medical Monitor.

5.1.5.3 Chemotherapy Dose Modifications, Treatment Delays, or Treatment Discontinuation and Management of Specific Adverse Events

Dose modifications for carboplatin and etoposide are permitted for toxicity according to the prescribing information and local standard of care.

Dose modification guidelines are provided below.

Treatment with carboplatin or etoposide should be discontinued if a patient experiences any hematologic or non-hematologic Grade 3 or Grade 4 toxicity after two dose reductions or treatment is delayed for more than 63 days due to toxicities.

Hematologic Toxicity

At the start of each cycle, the ANC should be $\geq 1500/\mu$ L and the platelet count should be $\geq 100,000/\mu$ L. Treatment should be delayed for up to 63 days to allow sufficient time for recovery. Growth factors may be used in accordance with American Society of Clinical Oncology (ASCO) and NCCN guidelines (Smith et al. 2006; NCCN 2019) or as per institutional guidelines. Upon recovery, dose adjustments at the start of a subsequent cycle will be made on the basis of the lowest platelet and neutrophil values from the previous cycle (see Table 7). Increased frequency of lab assessments (e.g., neutrophil and platelet counts) on Cycle 1, Day 8 and Cycle 1, Day 15 are used to better characterize the impact of and response to treatment. Since such assessments are not routinely performed, they will not be used for dose modifications for subsequent cycles. Therefore, Cycle 2 dose adjustments will be based on assessments performed after Cycle1, Day 21.

In the event that dose adjustments are needed for both ANC and platelets, patients are to receive the lower dose.

Table 7 Chemotherapy Dose Modification for Hematologic Toxicities

Toxicity ^a	Dose	
ANC <500/µL and platelets ≥50,000/µL	75% of previous dose	
Platelets <25,000/μL, regardless of ANC	75% of previous dose	
Platelets $<$ 50,000/µL with Grade \ge 2 bleeding, regardless of ANC	50% of previous dose	
ANC < 1000/ μ L plus fever of \geq 38.5°C	75% of previous dose	

^a Nadir of prior cycle with the exception of Cycle 1, where neutrophil and platelet assessments performed after Cycle 1, Day 21 will be used for dose adjustment.

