Diarrhea, Grade 4	 Withhold venetoclax. Withhold atezolizumab plus carboplatin etoposide. Administer anti-diarrheals per institutional guidelines (e.g., loperamide 4 mg initial dose up to a maximum of 16 mg per day) Upon resolution of Grade 4 diarrhea to Grade ≤ 1: Resume treatment with venetoclax at one dose level reduction (see Table 7) Administer carboplatin and etoposide at 75% of previous dose (see Table 8). Dose of carboplatin and etoposide can be re-escalated (even to full dose) with the approval of Medical Monitor (see Section 5.1.5.2). Administer atezolizumab at previous dose. For uncontrolled Grade 4 diarrhea that occurs despite adequate anti-diarrhea medication or any grade of diarrhea requiring hospitalization: Further reduce venetoclax by one dose level (see Table 7). Administer carboplatin and etoposide at 75% of previous dose (see Table 8).
Hepatic event, Grade 2	 Monitor LFTs more frequently until return to baseline Events of > 5 days duration: Withhold atezolizumab for up to 12 weeks after event onset. Initiate treatment with corticosteroids equivalent to 1–2 mg/kg/day oral prednisone. If event resolves to Grade 1 or better, resume atezolizumab. If event does not resolve to Grade 1 or better while withholding atezolizumab, permanently discontinue atezolizumab and contact Medical Monitor.

Table 10Management Guidelines for Specific Adverse Events with
Venetoclax, Atezolizumab, and Carboplatin Etoposide (cont.)

Table 10 Management Guidelines for Specific Adverse Events with Venetoclax, Atezolizumab, and Carboplatin Etoposide (cont.)

Event	Management	
Hepatic event, Grade 3	 Discontinue atezolizumab. Withhold venetoclax. Withhold carboplatin and etoposide. If hepatic event resolves to ≤ Grade 1: Resume venetoclax at one dose level reduction (see Table 6). Administer carboplatin and etoposide at 75% of previous dose (see Table 8). 	
Hepatic event, Grade 4	Discontinue atezolizumab.Discontinue venetoclax.Discontinue carboplatin and etoposide.	

ANC = absolute neutrophil count; G-CSF = growth-colony stimulating factor.

^a Dose modifications (as specified in the table above) should be made based on ANC and platelet count assessment on Day 1 of each cycle. No dose modifications are required based on ANC and platelet count assessment done on Cycle 1, Day 8 and Cycle 1, Day 15.

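### For carboplatin and etoposide at Cycles 3 and 4, Table 7 reduces on the prior-cycle nadir and Table 10 on the Day 1 count, with no stated precedence; platelets below 25,000 with bleeding also fall in two Table 7 rows

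*Combined protocol and SAP*

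**What the plan says.** **Nadir basis.** Section 5.1.5.3 says that, after recovery, chemotherapy adjustments "will be made on the basis of the lowest platelet and neutrophil values from the previous cycle". Table 7 footnote a repeats the rule: "Nadir of prior cycle with the exception of Cycle 1". For the Cycle 2 dose, only counts taken after Cycle 1 Day 21 are used.

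**Day 1 basis.** Table 10 (Section 5.1.6.3) carries its own footnote a on the Grade 3 and Grade 4 neutropenia rows and the Grade 4 thrombocytopenia row. It says that the modifications listed in that table "should be made based on ANC and platelet count assessment on Day 1 of each cycle", and it sets aside the Cycle 1 Day 8 and Day 15 counts. Both Grade 4 rows put carboplatin and etoposide at 75% of the previous dose, with a reference to Table 7.

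**Which table leads.** Section 3.3.2.3 states: "The dose of carboplatin and etoposide should be reduced per standard guidance provided in Table 7". Section 5.1.6.3 directs sites to Sections 5.1.5.1 to 5.1.5.3 and to Table 10 together, without ranking them.

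**Platelet rows.** Table 7 gives 75% for platelets below 25,000 whatever the ANC. It gives 50% for platelets below 50,000 with Grade 2 or higher "bleeding, regardless of ANC". Table 10 gives 75% for Grade 4 thrombocytopenia and 50% for Grade 3 thrombocytopenia with Grade 2 or higher bleeding.

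**The concern.** Two dosing rules for the same cytotoxic drugs name different blood counts as the trigger. Two sites reading the protocol carefully could give different chemotherapy doses to patients with the same blood counts. Whether a reduction is triggered also matters later, because Section 5.1.5.3 stops carboplatin or etoposide for Grade 3 or 4 toxicity after two reductions.

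The situation can arise on scheduled data. Appendix 2 places hematology on Day 15 of Cycles 2 to 4 in Arm B escalation, and Section 3.3.2.2 expects overlapping cytopenias. In an induction expansion, Appendix 2 footnote c makes Day 15 assessments unnecessary, so there the conflict needs an unscheduled count.

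The platelet rows raise a second problem: as written, Table 10 makes the smaller chemotherapy cut for the worse platelet count.

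**Working it through.** The plan gives no figure to reproduce. The check applies each rule to the same patient.

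**Inputs.** Induction has four cycles, with carboplatin AUC 5 and etoposide 100 mg/m² (Section 4.3.2). A cycle starts only with ANC at least 1500/µL and platelets at least 100,000/µL (Section 5.1.5.3). Table 7's first row is ANC below 500/µL "and platelets ≥50,000"/µL, at 75%.

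**Step 1: Cycle 2 dose.** Table 7 uses counts after Cycle 1 Day 21. Table 10 uses the Day 1 count and ignores Cycle 1 Days 8 and 15. The two agree in effect.

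**Step 2: Cycle 3 dose.** Suppose Cycle 2 was given at full dose and its Day 15 count showed ANC below 500 with platelets at least 50,000, or platelets below 25,000 without bleeding. By Cycle 3 Day 1, ANC is at least 1500 and platelets are at least 100,000.

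- Table 7: 0.75 × AUC 5 = AUC 3.75, and 0.75 × 100 = 75 mg/m².
- Table 10: the Day 1 count is not Grade 4, so the row is not triggered. Read alone, the table leaves AUC 5 and 100 mg/m².

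**Step 3: Cycle 4 dose.** The same split follows from a recovered Cycle 3 nadir. A Cycle 4 nadir precedes no further chemotherapy, so the exposed decisions are those for Cycles 3 and 4.

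**Step 4: platelets with Grade 2 or higher bleeding.**

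| Platelets/µL | Table 7 | Table 10 |
|---|---|---|
| 25,000 to below 50,000 | 50% | 50% |
| below 25,000 | 75% row and 50% row both met | 75% |

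From full dose, 75% is AUC 3.75 and 75 mg/m²; 50% is AUC 2.5 and 50 mg/m². No tie-break fits. The sentence that "patients are to receive the lower dose" covers adjustments needed for both ANC and platelets, not two platelet rows. The highest-grade rule in Section 5.1.5, if applied here, selects the Grade 4 row, which is the smaller cut.

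**The case against.** **The documents already lead to Table 7.** Section 3.3.2.3 sends chemotherapy there, and Table 10's Grade 4 rows refer to it. This largely stands. A reader might infer that Table 10 orders full-dose chemotherapy after a recovered nadir. It does not: an untriggered row orders nothing, and Table 7 still applies. But footnote a covers every modification in its rows, chemotherapy included. The cross-reference supplies the dose, while the footnote fixes which count triggers it.

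**Sites have latitude.** Section 5.1.5.3 allows modification "according to the prescribing information and local standard of care", and Section 5.1.5 gives investigators discretion. Some variation is therefore accepted. Discretion to depart from a rule does not say which of two triggers is the rule.

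**A nadir basis cuts against sparing chemotherapy.** Section 3.3.2.3 aims to preserve the dose intensity of atezolizumab, carboplatin and etoposide. If chemotherapy followed the nadir and venetoclax the Day 1 count, a recovered Grade 4 count would reduce chemotherapy and leave venetoclax at full dose. This stands, and the fix has to deal with it. It does not show that Day 1 was meant for chemotherapy: both texts exclude by name only the Cycle 1 Day 8 and Day 15 counts, and a general Day 1 rule would leave Table 7's nadir basis without a purpose.

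**The bleeding row is the more specific one.** It covers everything below 50,000, so it reasonably takes in counts below 25,000. That supports 50% as the intended answer, but Table 10's Grade 4 row still says 75%.

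**Conclusion.** The protocol is inconsistent on which count governs carboplatin and etoposide at Cycles 3 and 4, mainly in Arm B escalation. The weight of the text favours the nadir, but precedence is not stated. Per affected decision the difference is 75% versus 100% of the previous dose, or 50% versus 100% if the bleeding row applies. This assumes a Grade 4 count that is measured mid-cycle and has recovered by Day 1; the documents do not say how often that will happen.

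The count conflict is confined to the rows that carry footnote a. The febrile neutropenia row and the Grade 3 thrombocytopenia with bleeding row do not carry it. The overlap for platelets below 25,000 with bleeding is a separate defect and does not depend on which count is used.

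A reader might infer consequences for the MTD, for response, or for overall chemotherapy intensity. The documents do not support these. The DLT window closes on Cycle 2 Day 1, before the rules diverge. Efficacy is analysed in expansion patients only (Section 6.5), for whom Day 15 counts are not required. A cumulative loss of dose cannot be estimated without the frequency of recovered Grade 4 nadirs and of approved re-escalation.

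**What to change.** 1. Amend Table 10 footnote a to say that carboplatin and etoposide reductions follow Table 7 footnote a: the prior-cycle nadir, with the Cycle 1 Day 8 and Day 15 counts not used.
2. In the same amendment, have the sponsor confirm whether venetoclax is also reduced on that nadir, so that chemotherapy is not cut while venetoclax stays at full dose, contrary to Section 3.3.2.3. This also bears on re-escalation, which Section 5.1.5.3 ties to cytopenias improving after a venetoclax reduction.
3. State in both tables that any platelet count below 50,000/µL with Grade 2 or higher bleeding, including counts below 25,000/µL, takes the 50% row.

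**Cost.** These are wording changes, with no added visits or samples. The clinical cost is that some patients with recovered Grade 4 counts receive 75% rather than 100% of the previous dose. Re-escalation approved by the Medical Monitor, already provided for, can offset that.

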5.2 SAFETY PARAMETERS AND DEFINITIONS

Safety assessments will consist of monitoring and recording adverse events, including serious adverse events and adverse events of special interest, performing protocol-specified safety laboratory assessments, measuring protocol-specified vital signs, and conducting other protocol-specified tests that are deemed critical to the safety evaluation of the study.

Certain types of events require immediate reporting to the Sponsor, as outlined in Section 5.4.

5.2.1 Adverse Events

According to the ICH guideline for Good Clinical Practice, an adverse event is any untoward medical occurrence in a clinical investigation subject administered a pharmaceutical product, regardless of causal attribution. An adverse event can therefore be any of the following:

- Any unfavorable and unintended sign (including an abnormal laboratory finding), symptom, or disease temporally associated with the use of a medicinal product, whether or not considered related to the medicinal product
- Any new disease or exacerbation of an existing disease (a worsening in the character, frequency, or severity of a known condition) (see Sections 5.3.5.9 and 5.3.5.10 for more information)
- Recurrence of an intermittent medical condition (e.g., headache) not present at baseline

Venetoclax—F. Hoffmann-La Roche Ltd Page 118 of 214 Protocol GO41864, Version 2

- Any deterioration in a laboratory value or other clinical test (e.g., ECG, X-ray) that is associated with symptoms or leads to a change in study treatment or concomitant treatment or discontinuation from study treatment
- Adverse events that are related to a protocol-mandated intervention, including those that occur prior to assignment of study treatment (e.g., screening invasive procedures such as biopsies)

5.2.2 Serious Adverse Events (Immediately Reportable to the Sponsor)

A serious adverse event is any adverse event that meets any of the following criteria:

- Is fatal (i.e., the adverse event actually causes or leads to death)
- Is life threatening (i.e., the adverse event, in the view of the investigator, places the patient at immediate risk of death)

This does not include any adverse event that, had it occurred in a more severe form or was allowed to continue, might have caused death.

- Requires or prolongs inpatient hospitalization (see Section 5.3.5.11)
- Results in persistent or significant disability/incapacity (i.e., the adverse event results in substantial disruption of the patient's ability to conduct normal life functions)
- Is a congenital anomaly/birth defect in a neonate/infant born to a mother exposed to study treatment
- Is a significant medical event in the investigator's judgment (e.g., may jeopardize the patient or may require medical/surgical intervention to prevent one of the outcomes listed above)

The terms "severe" and "serious" are not synonymous. Severity refers to the intensity of an adverse event (e.g., rated as mild, moderate, or severe, or according to NCI CTCAE; see Section 5.3.3); the event itself may be of relatively minor medical significance (such as severe headache without any further findings).

Severity and seriousness need to be independently assessed for each adverse event recorded on the eCRF.

Serious adverse events are required to be reported by the investigator to the Sponsor immediately (i.e., no more than 24 hours after learning of the event; see Section 5.4.2 for reporting instructions).

5.2.3 Adverse Events of Special Interest (Immediately Reportable to the Sponsor)

Adverse events of special interest are required to be reported by the investigator to the Sponsor immediately (i.e., no more than 24 hours after learning of the event; see Section 5.4.2 for reporting instructions). Adverse events of special interest for this study are as follows:

- Cases of potential drug-induced liver injury that include an elevated ALT or AST in combination with either an elevated bilirubin or clinical jaundice, as defined by Hy's Law (see Section 5.3.5.7)
- Suspected transmission of an infectious agent by the study treatment, as defined below

Any organism, virus, or infectious particle (e.g., prion protein transmitting transmissible spongiform encephalopathy), pathogenic or non-pathogenic, is considered an infectious agent. A transmission of an infectious agent may be suspected from clinical symptoms or laboratory findings that indicate an infection in a patient exposed to a medicinal product. This term applies only when a contamination of study treatment is suspected.

- Pneumonitis
- Colitis
- Endocrinopathies: diabetes mellitus, pancreatitis, adrenal insufficiency, hyperthyroidism, and hypophysitis
- Hepatitis, including AST or ALT > 10 × ULN
- Systemic lupus erythematosus
- Neurological disorders: Guillain-Barré syndrome, myasthenic syndrome or myasthenia gravis, and meningoencephalitis
- Events suggestive of hypersensitivity, infusion-related reactions, cytokine-release syndrome, influenza-like illness, and systemic inflammatory response syndrome
- Nephritis
- Ocular toxicities (e.g., uveitis, retinitis, optic neuritis)
- Myositis
- Myopathies, including rhabdomyolysis
- Grade \geq 2 cardiac disorders (e.g., atrial fibrillation, myocarditis, pericarditis)
- Vasculitis
- Autoimmune hemolytic anemia
- Severe cutaneous reactions (e.g., Stevens-Johnson syndrome, dermatitis bullous, toxic epidermal necrolysis)
- Tumor Lysis Syndrome
- Grade 4 thrombocytopenia

Venetoclax—F. Hoffmann-La Roche Ltd

Page 120 of 214 Protocol GO41864, Version 2

• Grade 4 Febrile neutropenia

5.3 METHODS AND TIMING FOR CAPTURING AND ASSESSING SAFETY PARAMETERS

The investigator is responsible for ensuring that all adverse events (see Section 5.2.1 for definition) are recorded on the Adverse Event eCRF and reported to the Sponsor in accordance with instructions provided in this section and in Sections 5.4-5.6.

For each adverse event recorded on the Adverse Event eCRF, the investigator will make an assessment of seriousness (see Section 5.2.2 for seriousness criteria), severity (see Section 5.3.3), and causality (see Section 5.3.4).

5.3.1 Adverse Event Reporting Period

Investigators will seek information on adverse events at each patient contact. All adverse events, whether reported by the patient or noted by study personnel, will be recorded in the patient's medical record and on the Adverse Event eCRF.

After informed consent has been obtained but prior to initiation of study treatment, only serious adverse events caused by a protocol-mandated intervention (e.g., invasive procedures such as biopsies, discontinuation of medications) should be reported (see Section 5.4.2 for instructions for reporting serious adverse events).

After initiation of study treatment, all adverse events will be reported until 30 days after the last dose of study drug or until initiation of new systemic anti-cancer therapy, whichever occurs first, and serious adverse events and adverse events of special interest will continue to be reported until 90 days after the final dose of study treatment or until initiation of new systemic anti-cancer therapy, whichever occurs first.

Instructions for reporting adverse events that occur after the adverse event reporting period are provided in Section 5.6.

5.3.2 Eliciting Adverse Event Information

A consistent methodology of non-directive questioning should be adopted for eliciting adverse event information at all patient evaluation timepoints. Examples of non-directive questions include the following:

"How have you felt since your last clinic visit?"

"Have you had any new or changed health problems since you were last here?"

5.3.3 Assessment of Severity of Adverse Events

The adverse event severity grading scale for the NCI CTCAE (v5.0) will be used for assessing adverse event severity. Table 11 will be used for assessing severity for adverse events that are not specifically listed in the NCI CTCAE.

Table 11 Adverse Event Severity Grading Scale for Events Not Specifically Listed in NCI CTCAE

Grade	Severity
1	Mild; asymptomatic or mild symptoms; clinical or diagnostic observations only; or intervention not indicated
2	Moderate; minimal, local, or non-invasive intervention indicated; or limiting age-appropriate instrumental activities of daily living ^a
3	Severe or medically significant, but not immediately life-threatening; hospitalization or prolongation of hospitalization indicated; disabling; or limiting self-care activities of daily living ^{b, c}
4	Life-threatening consequences or urgent intervention indicated ^d
5	Death related to adverse event ^d

NCI CTCAE=National Cancer Institute Common Terminology Criteria for Adverse Events. Note: Based on the most recent version of NCI CTCAE (v5.0), which can be found at: http://ctep.cancer.gov/protocolDevelopment/electronic_applications/ctc.htm

- ^a Instrumental activities of daily living refer to preparing meals, shopping for groceries or clothes, using the telephone, managing money, etc.
- ^b Examples of self-care activities of daily living include bathing, dressing and undressing, feeding oneself, using the toilet, and taking medications, as performed by patients who are not bedridden.
- ^c If an event is assessed as a "significant medical event," it must be reported as a serious adverse event (see Section 5.4.2 for reporting instructions), per the definition of serious adverse event in Section 5.2.2.
- ^d Grade 4 and 5 events must be reported as serious adverse events (see Section 5.4.2 for reporting instructions), per the definition of serious adverse event in Section 5.2.2.

